### Efficacy Analyses

All hypothesis tests for main effects will use a 2-sided test at the 5% level of significance.

---

### Primary Efficacy Analysis

The primary endpoint is the rate of new stroke (both ischemic and hemorrhagic) reported during the 3-month treatment period.

#### **Main Model**

The time to first new stroke (both ischemic and hemorrhagic) reported during the 3-month treatment period for the ITT Population will be summarized by treatment group using Kaplan-Meier estimates. The hazard ratio for the treatment comparison will be derived using a Cox's proportional hazards model, including the pooled study center as a random effect. The hazards ratios with 95% CI will be reported.

This will also be presented graphically on a Kaplan-Meier plot.

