### 7.6.2 Method of assigning patients to a treatment group

The randomization code list will be generated centrally by a Contract Research Organization (CRO).

The patient kits will be packaged in accordance with this randomization code list. During the treatment period, the patient will receive study medication corresponding to either the clopidogrel / ASA group or the ASA group using a randomization ratio of 1:1.

Randomization will be stratified according to the time from symptoms onset to randomization (<12 hours or ≥12 hours).

The treatment number will be allocated using a centralized treatment allocation system (Inter-voiceResponse System, IVRS) on D1 (baseline visit). Before randomizing a patient, the investigator will have to contact the IVRS and give some information (such as study number, patient date of birth and initials, study site, and time between symptom onset and randomization). A treatment number will then be given to the investigator, who will give the first box of the corresponding package to the patient.

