#### 9.1.3 Randomization

The statistician will develop a master randomization list, with stratification blocked to assure an equal distribution of treatments at each participating site. If the subject was confirmed, the investigator will call the IVRS for randomization and treatment group allocation. This system will allow Clinical Sites to perform participant enrollment around the clock, 7 days a week. A study number will correspond to a specific medication packet. This identifying number will be coded on the enrollment confirmation.

#### 9.1.4 Treatment on DAY 1

The patient will receive Day 1 study medication and be instructed how to take the study medication. Time of first study drug administration will be recorded.

Study drug will be started as soon as possible after randomization (within 24 hours after onset).

ASA will be given at the discretion of the investigator, at a total dose for Day 1 between 75 and

300 mg.

The following information will be collected for each patient:

- ✓ Demographic (age, sex, ethnic origin)
- ✓ Patient's medical history and concomitant diseases
- ✓ Concomitant medications
- ✓ An appointment will be made for next study visit ( $D_{21} \pm 2$  days after randomization)

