### **Planned Analyses**

The analyses that are detailed in this SAP will be performed only when the database has been frozen, all protocol violators identified and treatment allocations have been unblinded. The treatment allocations will be unblinded and extracted from the RandAll system. These will then be merged on to the study database using the treatment number (as allocated to each subject by RAMOS) to match subjects with the correct treatment allocation. Membership of the Intent-to-Treat and Per Protocol populations will be determined using the rules set out in this SAP and will be determined prior to unblinding the treatment allocation. At a date to be agreed within the project team, a data look will be performed. This will involve production of all data displays on a subset of the data using dummy treatment codes. These are produced purely as an aide to the pre-programming of the study and no unblinding will occur.

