## 7.6.2 患者随机分组的方法

随机码列表将在合同研究组织（CRO）集中生成。

患者的药物将按照随机码表进行包装。在治疗期间，患者将接受氯吡格雷/阿司匹林组或者阿司匹林组的研究药物治疗，分配到两组的随机概率为1:1。

将根据随机化时发病时间是否超过12小时进行分层随机分组。

在第一天(基线随访)时随机顺序表将由计算机系统自动生成，受试者将按照入组的先后顺序，由小到大依次获得指定的随机试验药物编号，之后研究者将给患者与号码相应的药物。根据各中心的研究进展，可调配入选的病例数，但需要得到数据管理中心的确认。

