### 9.1.3 随机化

统计学家将制定一份专业的随机表，确保治疗药物在每一个参与中心平均分布。如果患者同意参与试验，研究者将根据患者入组的先后顺序取得对应随机号，该随机号将记录在入组筛选表及 CRF 表上。

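### The primary and secondary Cox models omit the onset-time stratum used at randomization (small numerical effect), and the Chinese protocol's order-of-entry numbering conflicts with IVRS allocation

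*Supplement*

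**What the plan says.** **Design.** Final English protocol 7.6.2: "Randomization will be stratified according to the time from symptoms onset to randomization", with the cut at 12 hours. The Chinese 7.6.2 has the same rule: "将根据随机化时发病时间是否超过12小时进行分层随机分组".

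**Analysis.** In the final SAP (Main Model) the primary hazard ratio is "derived using a Cox's proportional hazards model, including the pooled study center as a random effect". The protocol synopsis gives the same model. The SAP sections on combined vascular events and on death from any cause reuse it. Section 10.2.1 adds no stratum in either language. In the SAP, onset time appears only in the list of predefined subgroups, each with its own interaction model.

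**Source of the primary p-value.** The SAP's Main Model section promises a hazard ratio with a confidence interval but names no test. English 10.2.1 refers to Kaplan-Meier methods and hazard ratios. Chinese 10.2.1 names a log-rank test for efficacy and does not mention stratification.

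**Allocation.** English 7.6.2: "The treatment number will be allocated using a centralized treatment allocation system", the IVRS. English 9.1.3 also uses an IVRS call, from a master list "with stratification blocked to assure an equal distribution of treatments at each participating site". The Chinese synopsis uses the IVRS too. The body of the Chinese protocol does not. Its 7.6.2 says "受试者将按照入组的先后顺序，由小到大依次获得指定的随机试验药物编号" (numbers are given from lowest to highest in order of entry). Its 9.1.3 says "研究者将根据患者入组的先后顺序取得对应随机号" (the investigator obtains the number by order of entry). The SAP (Planned Analyses) names other systems: "The treatment allocations will be unblinded and extracted from the RandAll system", with treatment numbers from RAMOS.

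**The concern.** A factor that restricts the randomization normally belongs in the primary analysis. If the factor is prognostic and the arms are balanced on it, leaving it out of a Cox model pulls the hazard ratio slightly toward 1 and costs a little power. Here the one factor that 7.6.2 names as a stratum is missing from the main model, while center, which 7.6.2 does not name as a stratum, is in it. No reason is given. The stratum is supplied when the patient is randomized, so using it needs no new data.

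The allocation text matters for the same reason: the analysis should respect the restriction that was actually applied. An analyst working from these documents cannot tell whether patients were allocated by an IVRS within onset-time strata or took the next number at the site.

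**Working it through.** **1. Reproduce the plan's sample size.** Inputs from protocol 10.1.1: control risk p1 = 0.14, relative risk 0.78, two-sided alpha 0.05, power 0.90, 5% dropouts. Then p2 = 0.14 × 0.78 = 0.1092, and the mean risk is 0.1246.

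n per arm = [1.960 × √(2 × 0.1246 × 0.8754) + 1.282 × √(0.14 × 0.86 + 0.1092 × 0.8908)]² / (0.14 − 0.1092)² = 2,415 (rounded up).

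The total is 4,830, as in Table 2. With dropouts it is 4,830 × 1.05 = 5,072 (the plan's method), or 4,830 / 0.95 = 5,085. Both are below 5,100.

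**2. Cross-check on the time-to-event scale.** HR = ln(1 − 0.1092) / ln(1 − 0.14) = 0.767. Expected events = 5,100 × (0.14 + 0.1092) / 2 = 635. Power = Φ(√635 / 2 × |ln 0.767| − 1.960) = 0.918.

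**3. Effect of leaving the stratum out.** The documents give neither the split between strata nor the risk by onset time, so both are assumptions: a 50:50 split and stratum hazard ratios θ from 1 to 3. The setup was N = 5,100, arms balanced within stratum, exponential event times censored at 90 days, no center effect, no losses, and 4,000 runs per setting. With 90 days as the time unit, the baseline hazard h solves 0.5(1 − e^(−hθ)) + 0.5(1 − e^(−h)) = 0.14. Unstratified and stratified log-rank (score) tests were applied to the same simulated data. Each cell shows unstratified / stratified.

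| θ | Power at HR 0.767 | Type I error at HR 1 | Mean estimated HR (true 0.767) |
|---|---|---|---|
| 1 | 0.9188 / 0.9188 | 0.0450 / 0.0452 | 0.7681 / 0.7681 |
| 1.5 | 0.9190 / 0.9205 | 0.0480 / 0.0482 | 0.7676 / 0.7671 |
| 2 | 0.9135 / 0.9172 | 0.0535 / 0.0555 | 0.7686 / 0.7671 |
| 3 | 0.9078 / 0.9135 | 0.0475 / 0.0512 | 0.7717 / 0.7683 |

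The largest power difference is 0.9135 − 0.9078 = 0.0057, about 0.6 points. The largest shift in the hazard ratio is 0.7717 − 0.7683 = 0.0034. The Monte Carlo standard error of a type I error estimate is √(0.05 × 0.95 / 4,000) = 0.0034, so all eight estimates are compatible with 5%.

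**4. Allocation texts side by side.**

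| Place | Who or what gives the number | Onset-time stratum | Site balance |
|---|---|---|---|
| English 7.6.2 | IVRS, told site and onset time | Named | Not named |
| English 9.1.3 | IVRS | Not named | Blocked by site |
| Chinese synopsis | IVRS, told site and onset time | Not named | Not named |
| Chinese 7.6.2 | Next number in order of entry | Named | Not named |
| Chinese 9.1.3 | Next number in order of entry | Not named | Even by site |

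The first three rows are compatible. The last two give a different mechanism and no IVRS step. Numbering by order of entry can honour an onset-time stratum only if each stratum has its own list, and no such lists are described.

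**The case against.** The best case for leaving the plan alone is the table in step 3. If the stratum is not prognostic, nothing is lost. At a threefold difference in hazard the gain is under one point of power. Alpha and the 5,100 are safe either way, and no plausible trial conclusion would turn on the change. The simulation also compared log-rank tests without a center effect, so it approximates the recommended model rather than testing it. All of this stands, and it limits the point to a cheap improvement in specification.

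Some stronger readings are tempting, but the documents do not support them.

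- *The stratification does not happen at sites.* The Chinese 7.6.2 requires onset-time stratification in so many words. Ascending numbers within stratum-specific lists would deliver it. The text fails to describe such lists, but it does not prescribe a single sequence either.
- *There are three incompatible schemes.* English 7.6.2 and 9.1.3 both use the IVRS, which receives site and onset time. They can be read as one scheme: onset-time strata with blocks by site. Neither section says so, but they do not contradict each other.
- *Onset time was chosen because recurrence risk falls steeply with it.* No section gives a reason for the stratum or any risk by onset time.

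**Conclusion.** The point holds as a matter of specification. The primary and secondary Cox models omit the factor by which randomization is stratified. For stratum hazard ratios up to 3 and an even split, both assumed, the cost is at most about 0.6 points of power and a hazard-ratio attenuation below 0.01. A reader might infer that the primary test is invalid or the trial underpowered. The calculations show neither: type I error is not inflated, and the planned 5,100 reproduces.

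The allocation conflict is real but narrower than it may look. It lies between IVRS allocation (Chinese synopsis, English 7.6.2 and 9.1.3) and order-of-entry numbering (Chinese 7.6.2 and 9.1.3).

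**What to change.** 1. **Settle the allocation scheme first**, because the analysis stratum should be the one applied at randomization. State one scheme (IVRS, onset-time stratum, and site blocks if used) in English 7.6.2 and 9.1.3, the Chinese synopsis, and Chinese 7.6.2 and 9.1.3. Reconcile the RandAll and RAMOS systems named in the SAP with it.
2. **Amend the SAP's Main Model section.** Stratify the primary Cox model by the randomized onset-time stratum (<12 h, ≥12 h) and keep pooled center as the random effect. Do the same for the secondary Cox models.
3. **Name the source of the primary p-value:** the stratified Cox model. Bring the log-rank test in Chinese 10.2.1 into line with it.
4. **Keep the present model** as a sensitivity analysis.

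The cost is one two-level stratum that the trial already records, plus aligned wording. The sample size does not change.

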#### **10.1.1 Sample Size Estimates**

##### **10.1.1.1 Primary Null Hypothesis**

In patients with TIA or minor ischemic stroke treated with aspirin 75 mg/day, there is no difference in 90-day risk of stroke (ischemic or hemorrhagic) in those treated with a 3-month regimen of clopidogrel initiated with a loading dose of 300 mg followed by 75 mg/day compared to placebo when therapy is initiated within 24 hours of symptom onset.

The minimum necessary sample size in the trial is established by the requirement to detect the smallest expected, clinically meaningful treatment difference comparing the treatment with placebo. A relative risk reduction of 22% (relative risk [RR] with addition of clopidogrel is 0.78) is the smallest difference we will attempt to detect.

With a sample size of 5100 patients, we will have 90% power to detect a relative risk reduction of 22% with a two-sided alpha of 0.05, and 5% drop outs (medication non-adherence) (Table 2 and Figure 2). The sample size formula used was based on the usual comparisons of proportions in two groups. This formula should provide more conservative estimates given that we plan a survival analysis for the trial.

Table 2. Sample size calculations for various risks (12% to 17%) of outcome in control (ASA) group

Power	n without drop outs	n with 5% drop outs	Risk of outcome in treatment group	Risk of outcome in control group	Relative risk with addition of clopidogrel
0.8	2880	3024	13%	17%	0.78
0.8	3094	3249	12%	16%	0.78
0.8	3334	3501	12%	15%	0.78
0.8	3608	3788	11%	14%	0.78
0.8	3926	4122	10%	13%	0.78
0.8	4296	4511	9%	12%	0.78
0.9	3856	4049	13%	17%	0.78
0.9	4140	4347	12%	16%	0.78
0.9	4462	4685	12%	15%	0.78
0.9	4830	5072	11%	14%	0.78
0.9	5254	5517	10%	13%	0.78
0.9	5750	6038	9%	12%	0.78

[figure not shown]

Figure 2. Sample size calculations for various risks of outcome in control (ASA) group by 90% or 80% power

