10.1.1.1 Risk of outcome in placebo (ASA) group

Based on the pooled Northern California and Oxfordshire cohort study[62] and FASTER trial[56], the 90-day risk of the stroke recurrence risk in this group is about 14% among high-risk TIA (ABCD2 score > 4) or minor stroke patients treated with ASA within 24 hours of symptom onset.

Table 3. Risk estimation of outcome in placebo (ASA) group

Population	n	3-month Risks	
		Stroke	Stroke / MI / Death
All TIA 	2776	10.30%	12.14%

Excluding low-likelihood 	2325	11.87%	14.02%
ABCD  score in TIA 			
> 3	2067	12.58%	14.42%
> 4	1379	14.72%	16.75%
> 5	737	17.50%	19.94%
TIA and minor stroke 	194	10.8%	11.9%

[figure not shown]
 Based on the pooled Northern California and Oxfordshire cohort study.

 FASTER trial.

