### Statistical Hypotheses

The primary endpoint for this study will be the rate of new stroke (both ischemic and hemorrhagic) reported during the 3-month treatment period.

The null hypothesis of no difference in this rate between the two treatment groups will be tested using a two-sided test at the 5% level of significance

$$H_0: \lambda_1/\lambda_2 = 1$$

$$H_1: \lambda_1/\lambda_2 \neq 1$$

Where  $\lambda_1$  is the rate of new stroke over the 3-month treatment period in the group treated with Clopidogrel/ASA regimen and  $\lambda_2$  is the same endpoint in the group treated with ASA alone.

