### Demographic and Baseline Characteristics

The following demographic information will be listed and summarized for subjects in each treatment group: age, sex, body mass index (BMI). This will also be done for smoking history, stroke and TIA history, symptoms of the index event, past medical history, family history, alcohol use, pretreatment Rankin Score and NIHSS score.

Laboratory tests will be listed and summarized for subjects in each treatment group including serum creatinine, glycemia, neutrophil count, and platelet count.

Vital signs including supine systolic blood pressure, diastolic blood pressure, and heart rate will also be listed and summarized in each treatment group.

Qualifying TIA baseline ABCD score will be summarized by treatment group.

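### The primary Cox model uses none of the prognostic baseline factors the trial already collects; the planned analysis keeps its 90% power, but a small, nearly free gain is forgone

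*Supplement*

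**What the plan says.** The final SAP tests the primary hypothesis with a "two-sided test at the 5% level of significance". Under Main Model, the hazard ratio for time to first stroke is "derived using a Cox's proportional hazards model, including the pooled study center as a random effect". Section 10.2.1 of the final protocol names no covariate either.

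The SAP's objectives list age, index event, ABCD2 (4 against above 4), previous stroke, previous TIA, diabetes, baseline systolic pressure and time to randomization as subgroup factors. Each enters only its own interaction model (Interactions with Subgroups). The baseline section also summarizes "stroke and TIA history, symptoms of the index event, past medical history" by arm. Protocol 7.6.2 stratifies randomization by time from onset (under 12 hours, or 12 hours and more). That factor is not in the primary model.

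On size, protocol 10.1.1 states: "With a sample size of 5100 patients, we will have 90% power to detect a relative risk reduction of 22" percent. It adds: "The sample size formula used was based on the usual comparisons of proportions in two groups". The control risk comes from the section holding "Table 3. Risk estimation of outcome in placebo (ASA) group", which concludes that "the 90-day risk of the stroke recurrence risk in this group is about 14" percent.

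**The concern.** The sponsor used ABCD2-specific risks to choose the planning control risk, so the protocol itself treats the score as prognostic. The primary estimate makes no use of it, or of the other factors recorded at baseline.

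Two things follow when a Cox model omits prognostic factors. First, the marginal hazard ratio lies slightly closer to 1 than the hazard ratio conditional on those factors, so the test is slightly less powerful than an adjusted one. Second, if a strong predictor is imbalanced by chance, any adjustment not already in the SAP will be post hoc. What is at stake is a little power and some protection against later discretion. Validity is not in question.

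**Working it through.** **1. The plan's own figure.** Inputs from protocol 10.1.1: control risk p1 = 0.14, relative risk 0.78, so p2 = 0.1092; two-sided alpha 0.05; power 90%; mean risk p = 0.1246.

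n per arm = [1.960·√(2p(1−p)) + 1.282·√(p1(1−p1) + p2(1−p2))]² / (p1 − p2)² = 2,415 after rounding up, or 4,830 in total. Multiplied by 1.05 this is 5,072. Both match Table 2. After 5% loss, 5,100 × 0.95 = 4,845 patients remain and power is 90.1%. The stated 90% is reproduced with no covariate.

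**2. The gradient in Table 3.** The ABCD2 rows are nested, so they must be differenced.

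- Above 3: 2,067 × 12.58% = 260.0 events
- Above 4: 1,379 × 14.72% = 203.0 events
- Above 5: 737 × 17.50% = 129.0 events
- ABCD2 = 4: (260.0 − 203.0)/(2,067 − 1,379) = 57.0/688 = 8.3%
- ABCD2 = 5: (203.0 − 129.0)/(1,379 − 737) = 74.0/642 = 11.5%
- ABCD2 above 5: 17.5%

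The top-to-bottom ratio is 17.5/8.29 = 2.11. On the SAP's own split (above 4 against 4) it is 14.72/8.29 = 1.78. The printed eligible rows alone show only 17.50/12.58 = 1.39.

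**3. Planned hazard ratio.** ln(1 − 0.1092)/ln(1 − 0.14) = 0.7667. This is a marginal hazard ratio, because it is built from the overall risks. Expected events are 4,845 × 0.1246 = 604. Schoenfeld power is Φ(|ln 0.7667|·√604/2 − 1.96) = 90.4%.

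**4. Adjusting for one index event/ABCD2 factor.** The levels are minor stroke and TIA with ABCD2 4, 5 and above 5, with the TIA levels in the ratio 688:642:737. Stratum hazards are H = −ln(1 − risk). They are scaled so that the overall control risk stays 14%, and the conditional hazard ratio is solved so that the overall treated risk stays 10.92%. The TIA share and the minor-stroke risk (entered at 12.58% before scaling) are assumptions, since the documents give neither. The information gain is (ln HRcond/ln 0.7667)² − 1, and patients' worth is that gain × 5,100.

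| TIA share | Conditional HR | Schoenfeld power | Information gain | Patients' worth |
|---|---|---|---|---|
| 100% | 0.7652 | 90.4% to 90.8% | 1.5% | about 75 |
| 50% | 0.7660 | 90.4% to 90.6% | 0.7% | about 35 |
| 30% | 0.7663 | 90.4% to 90.5% | 0.4% | about 20 |

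Simulation (8,000 trials per row) gave gains of 0.3, 0.3 and 0.1 points, with Monte Carlo standard errors of 0.10 to 0.15. The standard error of the log hazard ratio does not fall (0.0821 unadjusted, 0.0822 adjusted). The gain comes only from the conditional hazard ratio being slightly further from 1.

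**5. All collected predictors together.** The documents give no risk by age, diabetes, prior events or blood pressure. As an assumption, let the combined log hazard be normal with SD 0.2 to 0.6, and hold 14% and 10.92% as before. Expected log-rank non-centrality then gives:

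| SD (assumed) | Conditional HR | Unadjusted power | Adjusted power | Information gain |
|---|---|---|---|---|
| 0.2 | 0.7661 | 90.1% | 90.3% | 0.5% |
| 0.3 | 0.7654 | 90.1% | 90.5% | 1.2% |
| 0.4 | 0.7644 | 90.1% | 90.7% | 2.2% |
| 0.5 | 0.7630 | 90.1% | 91.1% | 3.6% |
| 0.6 | 0.7611 | 90.1% | 91.6% | 5.5% |

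Before rounding, the gains run from 0.15 to 1.4 points. For scale, the ABCD2 gradient alone implies an SD of about 0.33 among TIA patients. An SD of 0.6 needs more than three times that variance.

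**The case against.** The strongest case against is that nothing here is an error. An unadjusted primary model with a center random effect is a legitimate prespecified choice, and its test is valid under randomization. It also targets a population-level effect, close to the protocol's endpoint of the percentage of patients with stroke. The gap between marginal and conditional hazard ratios is non-collapsibility and not bias. Chance imbalance is already reflected in the confidence interval and is small with about 2,400 patients per arm. All of this stands.

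A reader might infer that the trial discards power it has paid for. It does not: the sample size rests on unadjusted proportions, no covariate gain was budgeted, and the unadjusted analysis delivers 90.1%. A reader might also reach 88.7% for the planned analysis at an SD of 0.6. That comes from treating 0.767 as a conditional hazard ratio. The treated risk then becomes 10.99%, a relative risk of 10.99/14 = 0.785, which is no longer the planned 0.78. With the planned risks held, unadjusted power stays at 90.1% at every SD tried.

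Table 3 has limits too. Its ABCD2 rows cover TIA cohorts only, and the visit schedule scores ABCD2 only for TIA, so the table says nothing about the spread of risk among minor-stroke patients. A single factor with minor stroke as its own level deals with the missing score but does not supply that information.

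What survives is that the covariates are already collected and named, adjustment helps a little, and it can be prespecified only before unblinding.

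**Conclusion.** The point holds as an optional improvement. The plan's power claim is sound. What the documents themselves support is a forgone gain of about 0.1 to 0.4 power points, or about 20 to 75 of 5,100 patients. It depends on Table 3 carrying over to this population and on an assumed TIA share of 30% to 100%. The range of 0.15 to 1.4 points (0.5% to 5.5% of information) for all predictors together rests wholly on an assumed SD of 0.2 to 0.6, and its upper end should not be quoted alone.

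**What to change.** Before unblinding, amend Main Model in the SAP so that the primary Cox model includes these prespecified fixed covariates beside treatment and the center random effect:

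- index event/ABCD2 category (minor stroke; TIA with ABCD2 4, 5, and 6 or more)
- age, continuous
- prior stroke or TIA
- diabetes
- baseline systolic pressure, continuous
- the randomization stratum (under 12 hours, or 12 hours and more)

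State how a missing covariate value is handled, so that no patient leaves the primary analysis for that reason. Report the currently planned model as supportive. State that the adjusted hazard ratio is conditional on the covariates, and keep the Kaplan-Meier risks as the population-level summary.

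The cost is SAP wording and a little programming, with no new data and no change to the sample size. The price in interpretation is that the primary hazard ratio becomes a conditional one, which the sponsor should accept knowingly.
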